There are no FDA-approved medications for meth use disorders. Furthermore, there are no effective pharmacologic strategies for meth-using MSM without severe use disorders.^{67,68} Although a sizable proportion of meth users are episodic users who do not have severe use disorders,^{69,70} pharmacologic studies have focused on individuals with severe use disorders.^{70,71} While some behavioral interventions for MSM reduce substance use and HIV risk behaviors,^{68,72,73} they may benefit from adjuvant pharmacologic agents.^{74,75}

Naltrexone is a promising agent for meth use that blocks the rewarding effects of meth. Administration of meth enhances release of mRNA precursors for endogenous opioids that bind to μ -opioid receptors and increase extracellular dopamine levels.⁷⁶⁻⁷⁸ Naltrexone competitively blocks endogenous opioids from activating μ -opioid receptors⁷⁹ in the nucleus accumbens and ventral tegmental area, which mediate dopamine release. Thus, the opioid antagonism by naltrexone decreases the activity of the dopamine reward pathways, tempering the positive neurobiological effects of meth.⁷⁸⁻⁸¹

Naltrexone is effective in attenuating the positive subjective effects of meth intoxication—including quality of “high”, craving, and euphoria, supporting efficacy among current meth users.⁸²⁻⁸⁷ Meth is rapidly metabolized to amphetamine in the bloodstream and administration of oral naltrexone prior to amphetamine exposure significantly reduced both the subjective effects of amphetamine and craving for amphetamine among healthy and amphetamine-dependent humans in laboratory studies.^{87,88} Additionally, oral naltrexone was associated with reductions in both craving and subjective response to meth, and also significantly reduced the association *between* craving and subjective response to meth after meth administration.^{89,90} Four double-blind, placebo-controlled naltrexone trials have observed efficacy on subjective effects and craving.^{87-89,91}

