Preliminary Studies: Numerous studies published by [name] and the collaborating research team involving MSM have informed the proposed research.^{58,66,70,71,124,149-156} The study team has successfully enrolled multiple cohorts of non-treatment seeking MSM in non-abstinence-based pharmacologic and behavioral trials with excellent participation in study visits, procedures, and retention rates.^{66,124,125,150} Our previous research has also demonstrated that reductions in substance use can result in parallel reductions in HIV sexual risk behaviors.^{66,71} **Table 1** lists relevant studies conducted by our group. **Project iN (intermittent naltrexone) study:** The current proposal logically builds on this pilot study establishing the feasibility, acceptability and tolerability of ION among 30 meth-using MSM without severe use disorders (ClinicalTrials.gov Identifier: NCT01723384). Preliminary data were extremely promising with a 61% screen to enroll rate, 95% retention rate and 93% study completion rate, suggesting that conducting a larger efficacy study on ION is feasible among meth-using MSM without severe use disorders. In addition, MSM in the trial reported high acceptability for the study procedures: most were satisfied /highly satisfied with the study (76%), were very likely to participate in a future study (71%), and were very likely to recommend the study to a friend (71%). No one in the study had stopped medications because of adverse events, suggesting that this intervention is tolerable in this population. This pilot was not powered to detect efficacy. We recognize the need for caution when interpreting results of pilot studies for hypothesis testing, as well as the controversy on estimating treatment effects from pilot studies.^{157,158} Nevertheless, specifying and testing analyses on meth use and sexual behaviors in the context of our pilot work is an important step in determining the applicability of our measures and analyses for a larger formal efficacy trial. In *exploratory, intention-to-treat (ITT) analyses*, we noted a point estimate consistent with a protective *signal* in favor of naltrexone, compared to placebo, on meth use (RR = 0.82).¹⁰⁹ While this was not statistically significant, we recognize that in small trials such as ours, type II error (i.e., false negatives) is a bigger concern due to small samples sizes, as opposed to type I error (i.e., false positives).¹⁵⁸ Hence, we interpret this result with caution. The study also found that meth-using MSM who used at least 1 day per week had significantly greater reductions in meth-using days when treated with ION, compared to placebo in a sub-group analysis (RR = 0.78).¹⁰⁹ Finally, we also found that ION participants had greater reductions in serodiscordant receptive anal intercourse (RR = 0.15) and serodiscordant condomless receptive anal intercourse (RR = 0.11), compared to placebo.¹⁰⁹ Participants also reported taking study drug 64% of the days that they craved meth or anticipated meth use. While this study drug compliance rate is better relative to our other pharmacotherapy trials with daily dosing, it still indicates a gap in compliance that can be enhanced with an adherence intervention, such as EMI. Hence, these findings support the *feasibility, acceptability, tolerability, and potential utility of ION to treat MSM who use meth and reduce HIV-related risks.*

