- Students
- Staff of UCSF or affiliated institutions
- None of the above

11.6 * SPECIAL SUBJECT GROUPS: Check the populations that may be enrolled: (REQUIRED)

- Children / Minors
- Adult subjects unable to consent for themselves
- Adult subjects unable to consent for themselves (emergency setting)
- Subjects with diminished capacity to consent
- Subjects unable to read, speak or understand English
- Pregnant women
- Fetuses
- Neonates

Prisoners
 Economically or educationally disadvantaged persons
 None of the above

11.7 INCLUSION CRITERIA: Briefly describe the population(s) that will be involved in this study. Include anyone that data will be collected from or about (e.g. patients, healthy controls, caregivers, providers, administrators, students, parents, family members, etc.):

Inclusion Criteria: 1) cisgender male (male gender and sex assigned at birth); 2) age 18-70 years* (naltrexone's tolerability and safety has been demonstrated among older adults up to age 70^{166,167}); 3) self-reported condomless anal sex with men or missing PrEP or ART doses due to meth use in the prior three months while under the influence of meth; 4) self-reported meth use at least weekly; 5) positive meth sample via sweat patch or urine testing during screening; 6) mild, moderate, and severe meth use disorder as determined by DSM-V-SCID criteria; 7) interested in reducing meth use; 8) no current acute illness requiring prolonged medical care; 9) no chronic illness that is likely to progress clinically during trial; 10) able and willing to provide informed consent and adhere to visit schedule; 11) current CD4 count \geq 200 cells/mm³; or CD4 count of 100-199 cells/mm³ and HIV viral load $<$ 200 copies/mL (if living with HIV); 12) baseline CBC, total protein, albumin, glucose, alkaline phosphatase, creatinine, BUN, and electrolytes without clinically significant abnormalities as determined by study clinician in conjunction with symptoms, physical exam, and medical history.

11.8 EXCLUSION CRITERIA: List any exclusion criteria (e.g. reasons why someone would not be included in the study):

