**07/13/2021**

## Statistical Analyses

We will use generalized estimating equations (GEE) to estimate treatment effects on repeated study outcomes. Primary analyses will be by intention-to-treat (ITT). In prior trials, we had excellent visit retention and study completion. Nonetheless, in this high-risk population, missing data may be encountered. We will conduct sensitivity analyses imputing all missing urine samples as positive, adjusting for baseline correlates of missingness, and using inverse probability of censoring weights.

**Specific Aim 1:** *To determine the efficacy of ION vs. placebo in reducing meth use, as determined by the proportion of meth-positive urine tests.* As in our prior trial, a GEE Poisson model with robust standard errors will be used to compare weekly urine test results by treatment assignment; this provides easier-to-interpret risk ratios rather than odds ratios. The treatment effect of ION vs. placebo will be modeled as linearly increasing and summarized by the between-group difference in means at 12 weeks, net of any baseline difference.

**Minimum Detectable Effects (MDEs) with sample size:** Based on the prior trial (93% retention), we estimate that 90% of participants will be retained at 12 weeks, and within-subject correlation will be 0.45. Under these assumptions, the study sample of 54 participants will have 80% power in 2-sided tests with a type-I error rate of 5% to detect net between-group differences in the reduction in urine positivity of ~24 percentage points, equivalent to a relative rate reduction of 32%. We have observed similar reductions on meth use in ITT and subgroup analyses in prior trials. Therefore, we believe that the reductions in meth use we are powered to detect in this aim are reasonable to anticipate.

**Specific Aim 2:** *To determine the efficacy of ION vs. placebo in reducing meth-associated sexual risk behaviors.* We will use GEE Poisson models with robust standard errors to assess evidence that the intervention reduces HIV risk behaviors, including number of sex partners, and number of sex partners with whom meth is used.

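### The trial admits severe meth use disorder, but the only evidence cited for its 32% detectable effect is a pilot that enrolled no severe cases and saw reductions of 18-22%

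*Protocol*

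**What the plan says.** Protocol 11.7 admits all three grades of disorder: "mild, moderate, and severe meth use disorder as determined by DSM-V-SCID criteria". It also requires "self-reported meth use at least weekly".

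Protocol 8.5 describes the pilot as a study of "ION among 30 meth-using MSM without severe use disorders", and concludes that "conducting a larger efficacy study on ION is feasible among meth-using MSM without severe use disorders". Protocol 8.4 presents the same group as the treatment gap: "there are no effective pharmacologic strategies for meth-using MSM without severe use disorders". The pilot results in 8.5 are RR 0.82 in the intention-to-treat analysis, not significant, and RR 0.78 for meth-using days among men using at least one day a week.

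For Aim 1, the SAP and Protocol 11.3 give a detectable difference of about 24 points in urine positivity, equivalent to a 32% relative reduction. The SAP supports it with "We have observed similar reductions on meth use in ITT and subgroup analyses in prior trials"; 11.3 says the same. Both cite reference 109 alone, which is the pilot, and both conclude that the effect is a reasonable one to expect. Protocol 8.13 draws that conclusion from the pilot's 18-22%, but beside a different detectable difference (about 14.5 points, on sweat patches).

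Randomization is stratified by HIV serostatus only (8.9). The SCID is done at screening (Table 3), and a Severity of Dependence measure is collected at enrollment and months 1-3 (Table 4). Neither is assigned an analysis. The exploratory modifiers named in 8.13 are age, race/ethnicity and, for racial/ethnic minority men, co-morbidities.

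**The concern.** The sample size argument needs a reason to believe that the detectable effect could occur in the men who will be enrolled. The one source cited falls short in two ways: it contains nobody with severe disorder, and its reductions are smaller than the effect for which the trial is powered. The documents do not say what share of participants is expected to have severe disorder, what effect is expected in them, or why the criteria go beyond the group that 8.4 and 8.5 describe.

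At stake are an honest account of what 60 participants can show and the use of a baseline severity measure that will exist in any case. If severity is first examined after unblinding, that analysis will be post hoc.

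**Working it through.** **1. Inputs.** Detectable difference 24 points = 32% relative; two-sided 5%; 80% power; within-subject correlation 0.45; effect rising linearly to week 12; 54 participants (SAP; 90% of 60), so 36:18 at 2:1. Implied control positivity is 0.24/0.32 = 0.75, and ION 0.75 - 0.24 = 0.51.

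**2. The plan's own figure.** Assume 13 weekly measurements (weeks 0-12), exchangeable correlation, variance μ(1-μ), and a linear mean model with arm, time and arm-by-time, on the difference scale. The standard error (SE) of the week-12 contrast net of baseline is 8.5 points at 36:18. The detectable difference is (1.960 + 0.842) × SE = 23.9 points, and power at 24 points is 80%. Hand check with constant variances: the sum of squares of weeks 0-12 is 182, so SE² = (144 × 0.55/182) × (0.51 × 0.49/36 + 0.75 × 0.25/18) = 0.435 × 0.01736, SE = 8.7 points, detectable difference about 24. The stated figure reproduces at N=54.

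**3. The pilot against the powered effect.** Relative reductions: 1 - 0.82 = 18%; 1 - 0.78 = 22%; planned 32%. On 75% control positivity:

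- RR 0.78: 0.75 × 0.22 = 16.5 points; power = Φ(0.165/0.0848 - 1.96) = 49%.
- RR 0.82: 0.75 × 0.18 = 13.5 points; power = Φ(0.135/0.0845 - 1.96) = 36%.

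With all 60 analysed, these become 54% and 39%. The RR of 0.78 is for meth-using days, not urine positivity, so carrying it over is itself an assumption.

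**4. Severe cases.** The documents give neither the severe share s nor the fraction k of the effect that severe cases obtain, so both are varied. The overall difference is 0.24 × [1 - s(1 - k)] (N=54, control 75% in both groups):

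| Severe share | k = 0 | k = 0.5 | k = 1 |
|---|---|---|---|
| 25% | 56% | 69% | 80% |
| 50% | 30% | 56% | 80% |
| 75% | 11% | 43% | 80% |

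The stated 80% is the right-hand column, an equal effect across severity. The plan does not state that assumption.

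**5. What a severity subgroup could show.** With half severe, each stratum has 18:9. The SE per stratum is 12.1 points, giving a 95% interval of about ±24 points (1.96 × 12.1). The SE of the difference between strata is 12.1 × √2, giving about ±33. A difference in effect would need to be about 48 points (2.80 × 12.1 × √2) to be detected with 80% power.

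**6. Chance imbalance.** With 40:20, the exact binomial probability that the severe share differs between arms by at least 20 points is 0.135 at a 30% or 70% share and 0.171 at 50%. If severe cases improved 20 points less (assumed), a 20-point imbalance would move the contrast by 0.20 × 0.20 = 4 points. That is 4/8.5 = 0.47 SE.

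**The case against.** **Broad eligibility is a legitimate choice, and the populations overlap.** Mild and moderate cases are common to both studies, and the weekly-use criterion matches the pilot subgroup with RR 0.78. This stands: the trial population is broader than the pilot's, not a different one.

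**Naltrexone has been tested in dependent users.** Protocol 8.4 cites a daily-naltrexone trial in 80 amphetamine-dependent adults (d = 0.5) and laboratory work in amphetamine-dependent people. So the k = 0 column is an extreme with no support in the documents. But that trial used another regimen in another population, and neither source is cited for the detectable effect.

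**The direction is unknown.** If severe cases raised control positivity to 85%, power at RR 0.78 would be 72% rather than 49%. This also stands; the point is that the equal-effect assumption is unstated, not that power must fall.

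**Severity is not wholly overlooked.** It is measured, the list of modifiers in 8.13 is not closed, and the adjustment for baseline correlates of missingness could include it. But nothing names it.

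Four stronger readings are tempting and do not hold:

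- A reader might infer that severity will probably be imbalanced between arms. A 20-point imbalance has a 13-17% chance; its assumed effect is under half an SE and random in direction, so it is ordinary randomization noise that the test already allows for.
- A reader might infer that a severity subgroup would tell a drug that fails from one that fails only in severe disorder. At ±24 points per stratum it could not.
- A reader might infer that severe participants would take the drug daily. No passage links SCID severity to daily craving, and the weekly supply is the same for everyone.
- A reader might treat a mild/moderate estimate as directly comparable with the pilot. The pilot ran 8 weeks, and the momentary reminders were added afterwards to improve adherence.

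**Conclusion.** The point holds in limited form. The cited pilot contains no severe cases and saw 18-22% against the 32% in the SAP and Protocol 11.3, so the statements that similar reductions have been seen and that the effect can reasonably be expected are unsupported as written. The smaller pilot effect is the firmer part: it needs no assumption about severe disorder and corresponds to 36-49% power at N=54. The severity part is conditional, with power for the 32% effect anywhere from 11% to 80% over the ranges shown. All of this assumes 75% control positivity, exchangeable correlation of 0.45 and a linear effect.

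The documents do not show that the trial is biased or that admitting severe disorder is wrong. The arithmetic behind the 24 points is sound at N=54; what fails is the evidence offered for it.

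**What to change.** Before unblinding:

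1. In Protocol 8.13 and 11.3 and in the SAP, replace the supporting sentences. Say that the pilot reductions were 18-22%, came from men without severe disorder and give no estimate for severe disorder, and that the 32% detectable effect therefore exceeds the pilot evidence and assumes an equal effect across severity. Protocol 8.13 carries a different detectable difference; reconcile it at the same time so that the statement refers to one figure.
2. Pre-specify baseline SCID severity (severe versus mild/moderate) and severity-by-time as covariates in the Aim 1 model or in a supporting adjusted analysis. The gain in precision is small unless severity strongly predicts change over 12 weeks.
3. Add severity to the exploratory modifiers named in 8.13. Estimate the ION effect by severity through arm-by-severity-by-time terms and their lower-order terms, report confidence intervals, and label the result descriptive, giving the expected width from step 5.

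The cost is wording, two covariate terms and one exploratory model; the SCID is already done at screening. The justification will read less favourably. Eligibility, dosing, visits and sample size are unchanged.

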Study medication: The Safeway Compounding Pharmacy, which currently prepares our study drug for our ongoing clinical trials, will provide the study drug kits for the proposed trial. Drugs are over-capsuled in a locking capsule to ensure the same appearance across all study arms and maintain double-blind. Study medications will be dispensed by the study clinician in MEMS® capped bottles with dosing instructions, date of dispensing, prescribing clinician, a 24-hour telephone study phone number for medical emergencies [contact]), and advisements against drug combinations. **Training on targeted dosing:** Participants will be trained on targeted medication dosing during enrollment and be provided an instructional leaflet for reference. They will be instructed to take 1 tablet when they believe that meth use risk is high or when meth use is imminent.¹⁰⁹ Participants will be given seven 50mg tablets per week and will be instructed to not exceed 1 tablet every 24 hours.¹⁰⁹ Based on concordance in adherence measures (self-report, pill count, and electronic monitoring) in our *double-blind* trials, we are confident that very little, if any, sharing of study medications is occurring between *blinded* participants.^{168,169} As a precaution, participants will be briefed about the importance of not sharing medications.

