Sweat Testing: We will utilize tamper evident sweat patches (PharmChem, Inc., Fort Worth, Texas) that absorb perspiration 24 hours a day, for up to 10 days of continuous wear.¹⁸⁷ These patches will be tested for the presence of meth and meth metabolites, using testing procedures approved by the FDA since 1995.¹⁸⁷ PharmChek patch enzyme immunoassays to detect meth in sweat have been found to have 85% sensitivity and a 93% specificity rates, compared to gas chromatography-mass spectrometry.¹⁸⁸ At screening visits, we will affix patches on all participants. These patches have a semi-permeable membrane to allow oxygen, carbon dioxide and water vapor to pass through the patch, keeping the skin underneath sterile and healthy. We will replace the used patch worn since the prior visit and send those used patches for meth testing to PharmChem's laboratories. These patches will retain meth and meth metabolites for any use during the period it was worn. Hence, we anticipate no gaps in the window of detection for meth use.

PrEP and ART adherence: Among HIV-negative participants on PrEP and HIV-positive participants on ART, we will collect 20 ml. urine samples and test drug levels using a Urine Tenofovir immunoassay and RNA viral load from blood samples collected at baseline and monthly follow-up visits. For PrEP, good adherence will be defined as having tenofovir-diphosphate (TFV-DP) concentration of 1500 ng/ml, which has been classified as evidence of consistent dosing.^{182,183 184} Good ART adherence among participants living with HIV will be defined as having undetectable HIV viral load below 50 copies/ml.

Study drug adherence: The study will collect self-reported adherence via weekly modified TLFB assessments, similar to prior targeted naltrexone studies^{106,209} and via EMA for all participants.¹⁰⁹ Pill counts at weekly visits will also assess adherence. **MEMS caps** will be used to track medication adherence daily for as-treated analyses; each cap opening is recorded as an event in real time. MEMS have been shown to be reliable for adherence monitoring and have been used in our studies.^{66,124 109}

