Exclusion Criteria: 1) any psychiatric (e.g., depression with suicidal ideation) or medical condition that would preclude safe participation; 2) known allergy or prior adverse reaction to naltrexone; 3) current use of any opioids or a known medical condition which currently requires or may likely require opioid analgesics; 4) opioid-positive urine test at screen/enrollment visits (naltrexone can induce opioid withdrawal); 5) moderate or severe liver disease (AST, ALT, or total bilirubin \geq 3 times upper limit of normal); 6) impaired renal function (creatinine clearance $<$ 60 ml /min); 7) currently participating in another intervention research study with potential overlap; 8) severe alcohol use disorder as determined by DSM-V SCID criteria; 9) any condition that, in the PI and/or study clinician's judgment interferes with safe participation or adherence to study procedures.

11.9 * RESEARCH CONDUCTED ON PATIENT CARE WARDS: Do any study activities take place on any patient care units including inpatient wards, peri- or post-operative care units, operating rooms, or in the Emergency Department at UCSF Health medical facilities: **(REQUIRED)**

Yes No

11.11 * EMERGENCY DEPARTMENT: Does your protocol or study involve any of the following patient related activities in the emergency department (e.g. subject identification, recruitment, consent, blood draws, specimen retrieval, involvement of ED staff (nursing, tech, and/or physician), or any other ED based procedures): **(REQUIRED)**

Yes No

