HIV and STI Testing risks. Participants may experience anxiety surrounding HIV testing results, regardless of the outcome. Positive results in particular may be stigmatizing, emotionally upsetting, and cause psychological distress. Testing will be done by a trained counselor and will include education on the meaning of results, risk-reduction counseling, and referral for treatment. Due to mandated reporting requirements, there could be a loss to confidentiality if there is a new case of HIV.

Naltrexone, Opiates and Fentanyl Risk: Naltrexone is a medication that blocks your body's ability to respond to opiate medicines or drugs, such as Oxycontin, methadone, or heroin. If you have taken opiates 7-10 days prior to taking naltrexone, there is a risk of mild to severe opiate withdrawal symptoms. If you take opiate medications for pain or are dependent on opiates for any reason. We have included a list of opioid medications in other study documents. If you are receiving naltrexone instead of placebo, you may not feel pain relief from opiate medications for 24 to 72 hours. This blocking effect can be overcome, but it must be done by an experienced physician, usually in the emergency room or hospital. If you take large amounts of opiates, including opiate-containing medications such as prescription pain pills (a guide will be given with

common names of opiate medications) or heroin, this can lead to overdose, including coma or death.

On the streets, dealers are mixing fentanyl with other drugs, such as heroin, cocaine, methamphetamine, and MDMA. Because fentanyl is cheap and very powerful, adding it to other drugs can be more profitable for dealers. This is especially risky when people taking drugs don't realize that fentanyl might be present in their drug supply. Fentanyl is known by such names as Actiq®, Duragesic®, and Sublimaze®. Street names for illegally used fentanyl include Apache, Dance Fever, Friend, Goodfellas, Jackpot, Murder 8, and Tango & Cash.

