Minimizing the risks of medication side effects. At all times, participants will be encouraged to contact the study clinician if they have questions or concerns about their medication dosage. During each study visit, participants are given the opportunity to discuss any adverse medication effects with the study clinician. Participants will have monthly safety blood tests, including liver function tests, during the 12 weeks they are taking study drug. Participants who ultimately do not tolerate their medication may be

taken of study medication if needed and will continue to be followed throughout the duration of the trial.

We will be testing potential participants for opiates, other substances and fentanyl during screening since naltrexone can cause opioid withdrawl. Participants who test positive for opiates or fentanyl will not be enrolled in the study. We will also test participants for opiates, other substances and fentanyl during monthly in-office safety visits and any positive results will not be given naltrexone.

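### The 7-10 day opioid withdrawal window that the protocol names is not carried into the entry criterion or into the hold after a positive test, and the hold does not cover tablets in hand or dosing prompts

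*Protocol*

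**What the plan says.** **Hazard.** Protocol 13.2 warns: "If you have taken opiates 7-10 days prior to taking naltrexone, there is a risk of mild to severe opiate withdrawal symptoms". I read this as use within the 7-10 days before a dose. The same section says that street methamphetamine may contain fentanyl without the user knowing.

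**Entry.** Protocol 11.8, criterion 3, excludes "current use of any opioids or a known medical condition which currently requires or may likely require opioid analgesics". Criterion 4 excludes an opioid-positive urine at screening or enrollment, and 13.3 extends this to fentanyl.

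**On study.** Section 13.3 repeats the testing "during monthly in-office safety visits and any positive results will not be given naltrexone". For participants taken off drug because they do not tolerate it, 13.3 says that they "will continue to be followed throughout the duration of the trial"; it does not say this for those with a positive test.

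**Dosing.** Section 8.9 sets the supply: "Participants will be given seven 50mg tablets per week and will be instructed to not exceed 1 tablet every 24 hours". On timing: "They will be instructed to take 1 tablet when they believe that meth use risk is high or when meth use is imminent". The bottle label carries "advisements against drug combinations". On unused tablets, the adherence text says only "Pill counts at weekly visits will also assess adherence". The EMA and EMI text sends a reminder to dose on days with high craving, stress or bad mood when no tablet has yet been taken.

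The SAP does not touch on this.

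**The concern.** The protocol names a hazard window in days, but the two rules that staff would apply do not use it. Nearby entry criteria are numeric (liver enzymes, creatinine clearance, CD4 count). The opioid criterion, which guards against a named drug interaction, relies on an undefined 'current use'.

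The hold in 13.3 governs what staff hand out. In this trial the participant decides when to dose, from tablets he already has, and a phone platform may prompt him to do so. Someone who has just tested positive for fentanyl could go home with unused tablets and be reminded to take one. What is at stake is avoidable withdrawal, mild to severe by the protocol's own description, in a participant on active drug.

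**Working it through.** No figure in the plan needs reproducing. The check sets the rules side by side, with simple arithmetic.

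**1. Entry.** Section 8.9 lists pre-randomization opioid testing twice. One list gives Screen 1, Screen 2 and Enrollment (3 tests). The other adds run-in 1 and run-in 2 (3 + 2 = 5 tests). To be randomized inside the 13.2 window, a man would need all of the following:
- opioid use within the last 7-10 days;
- not being judged a current user under criterion 3;
- negative results on all 3 to 5 tests;
- no exclusion by the clinician under criterion 1 or 9, although 13.3 has a clinician evaluate every candidate and 8.9 records medications for the 30 days before enrollment.

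Assay detection times and visit spacing are not given, so the probability of this combination cannot be calculated. No text makes the 30-day medication record an eligibility rule, so known recent use with negative tests is left to judgment.

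**2. On-study testing.** Of 12 weekly visits, 9 are remote (weeks 1-3, 5-7, 9-11), leaving 12 - 9 = 3 with opioid testing (weeks 4, 8, 12). Tests are 28 days apart, which is 28/10 = 2.8 to 28/7 = 4 times the window. The home kit described in 13.4 is for methamphetamine only. Opioid use is also self-reported by ACASI at enrollment and months 1-3 (Table 4), but 8.9 says staff will not see those data during the trial, so that report cannot trigger a hold. Weekly verbal review of medications and adverse events can.

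**3. Tablets in hand at a positive test.** In hand = supplied - taken.

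| Supply assumption | Supplied | In hand |
|---|---|---|
| Weekly, no carry-over | 7 | 0-7 |
| Four weeks at once, no carry-over | 7 x 4 = 28 | 0-28 |
| Carry-over, at week 4 | 7 x 4 = 28 | 0-28 |
| Carry-over, at week 8 | 7 x 8 = 56 | 0-56 |

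Section 8.3 lists drug dispensing among weekly-visit activities, but how tablets reach participants in remote weeks is not stated. The upper ends mean that no tablets were taken. As-needed dosing makes some leftovers likely, and no collection of unused tablets is described.

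**4. Dosing prompts.** The EMI triggers in 8.9 are craving, stress and mood, on days without a dose. No opioid exception is described. The message wording was not available.

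**5. Dosing time at issue.** The dosing period is 12 x 7 = 84 days. A 10-day interruption is 10/84 = 11.9% of it, and 7 days is 8.3%. If a retest had to wait for the next scheduled in-office visit, the interruption would be 28/84 = 33.3%.

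**The case against.** The strongest reply is that protection is layered. Besides the tests, criteria and clinician evaluation above, participants receive an opioid guide, weekly reminders of the interaction, labelled bottles and a 24-hour phone line. Clinicians review data forms daily (13.3) and safety issues weekly (14.1). Sweat patches are collected for other substances too (9.1), though opioids are not named on that panel. This stands, and it is why the entry gap is small. None of these measures sets an interval or deals with tablets in hand.

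A second reply is that the interval may be given elsewhere. The warning in 13.2 is addressed to the participant, which suggests consent wording, and the consent form, leaflet, study guide and prompt text were not available. A reader might infer that participants are never told to wait; the documents do not support that. Staff, however, apply eligibility and hold rules from the protocol, and a leaflet would not define those.

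A third concerns restarting. A reader might infer that 13.3 foresees a restart and leaves its timing open. It does not: read plainly, a positive test means that naltrexone stops, and no resumption is mentioned. A rule allowing restart on elapsed time alone would be weaker than this, because unknowing fentanyl exposure could continue undetected between in-office visits.

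**Conclusion.** The point holds as a cheap improvement to participant safety. Followed literally, the entry and hold rules allow dosing inside a window that the protocol itself describes as hazardous. The on-study part is the stronger: after a positive test nothing in the available text covers tablets in hand (0 to 56 by week 8 under carry-over, which is an assumption) or the prompts to dose. The entry part is minor, since several safeguards must fail together.

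A reader might infer that recent opioid users will be enrolled in numbers, or that the trial's results are affected. The documents support neither. The number affected cannot be derived, and no effect on power, type I error or the analysis is claimed. The conclusion rests on the protocol text alone; the unseen participant materials may already cover part of it.

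**What to change.** 1. **Protocol 11.8, criterion 3.** After the words on current use, insert *or any known use within the past 10 days*, and leave the rest of the criterion as it is. Ten days is the upper end of the 13.2 window. Ask the question at screening and at enrollment.
2. **Protocol 13.3.** After any positive opiate or fentanyl test, tell the participant to stop study drug and return the tablets he holds, switch off his EMI dosing prompts, and keep him in follow-up. Apply this identically in both arms, and write 'study drug' rather than 'naltrexone', since the trial is double-blind.
3. **Resumption.** Keep the present stop as the default. If resumption is allowed at all, require at least 10 opioid-free days, a negative in-office opioid and fentanyl retest, and study clinician clearance.
4. **Participant materials.** Check that the consent form, leaflet, study guide and prompt text agree with these rules.

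**Cost.** Wording in two sections, one added question and a check of materials. A few candidates are deferred by up to 10 days. A participant who tests positive loses dosing days: at least 10 of 84 (11.9%) if he resumes, or the rest of the dosing period if he does not, which the plain reading of 13.3 already implies for newly dispensed drug. A look-back question cannot catch unknowing fentanyl exposure, which still depends on urine testing.
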